5.2.2 Full Analysis Set

The FAS is defined as the subjects who received either at least one injection of CYD dengue vaccine or placebo and had at least one blood sample drawn and valid post-injection serology results (i.e. a result different from "not reportable" ["NR"] or missing, for at least one dengue serotype). Subjects will be analyzed by the vaccine group to which they were randomized.

5.2.3 Safety Analysis Set

The safety analysis set (SafAS) is defined as those subjects who have received either at least one injection of either CYD dengue vaccine or placebo^a. A safety analysis set is defined for each dose as the subset of subjects having received this dose; subjects will be analyzed according to the treatment received at this dose. For the analysis at any dose, subjects will be analyzed according to the treatment received at the first dose.

Safety data recorded for a vaccine received out of the protocol design will be excluded from the analysis (and listed separately).

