3.1 Trial Design

This observer-blind, randomized, Phase II non-inferiority trial will be conducted in 2 sequential stages.

At enrollment, for STAGE I, approximately 1050 healthy subjects between 9 and 50 years of age will be randomized (1:1:1) stratified by site (████, █████, █████, ██████████, █████ and █████) and age group (Children 9-11 years, Adolescents 12-17 years, Adults 18-39 years and Adults 40-50 years) to 1 of 3 treatment arms (Groups 1, 2, or 3) to receive 3 injections (in various schedules of CYD dengue vaccine and placebo administration) over a 12-month period (administered 6 months apart: at D0; D0 + 6 months; and D0 + 12 months).

For STAGE II, subjects randomized to each of the 3 treatment arms in STAGE I will also be randomized (1:1) to 1 of 2 subgroups (e.g., subgroup a or b). The subject's dengue serostatus at baseline, based on plaque reduction neutralization test (PRNT), will determine her/his eligibility to receive the booster injection. Only the subjects identified as dengue seropositive at baseline will receive a booster injection of CYD dengue vaccine at either 12 months (Subgroup a, Injection 3 + 12 months) or 24 months (Subgroup b, Injection 3 + 24 months) following the last primary series injection.

At each injection visit in STAGE I, subjects will receive a single dose of either CYD dengue vaccine (CYD) or placebo (PLA): Group 1 subjects (N = 350) will receive CYD dengue vaccine at all 3 injection visits; Group 2 subjects (N = 350) will receive PLA at the first injection visit and CYD dengue vaccine at the last 2 visits; and Group 3 subjects (N = 350) will receive PLA at the first 2 visits and CYD dengue vaccine at the last injection visit.

A total of 60 subjects (10 subjects in each of 6 subgroups) who consent to participate in additional immunological testing will also be included in a specific subset (AIT subset). It is to be noted that the 1:1 ratio per subgroup is unlikely to hold as only subjects dengue seropositive at baseline will be eligible to booster injection.

Blood samples will be taken at several time points throughout the study for CMI, neutralizing Ab, and Ab specificity and affinity maturation assessments. More details are provided in Section 5.1.3 of the protocol.

The duration of each subject's participation in the trial will be approximately 30 to 42 months.

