4.4.2.3 SAEs

4.4.2.3.1 Last Vaccination

Last vaccination before an SAE is derived from the last visit numbers provided in the clinical database and is calculated as follows:

- If an SAE has a non-missing visit number, the visit number should be used to determine the last vaccination before the SAE
- If the visit number is missing, then the start date should be used to determine the last vaccination before the SAE

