4.4.2.3.2 Time of Onset

Time of onset will be computed using the same methodology than for unsolicited non-serious AEs described in [Section 4.4.2.2.4](#).

SAEs will be analyzed throughout the study using the following periods:

- Within 28 days after injection
- During the study (i.e., all SAEs occurred during the study)

An SAE with missing time of onset will be considered to have occurred after the vaccination indicated by the visit number, so will be included in these tables. SAEs collected after Visits 1, 3, 5, 7, 8, or 9 with missing time of onset will be included in the table of SAEs analyzed “within 28 days” after the respective injection.

Note: SAEs that occurred before vaccination (negative time to onset) will not be included in analysis, but will be listed separately.

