5.1.2.2.2 Statistical Methods for Other Objectives

5.1.2.2.2.1 Immunogenicity

STAGE I:

In addition, immunogenicity will be assessed using the following parameters:

- Geometric means of the individual titer ratios (GMTR) for each serotype (parental strains) by baseline serostatus (1 year post-Dose 3 /28 days post-Dose 3)
- Group 1 only, GMTR for each serotype (parental strains) by baseline serostatus (28 days post-Dose 3 /post-Dose 2)

STAGE II:

- Seroconversion rates 28 days after the booster for each serotype (parental strains) of CYD dengue vaccine

5.1.2.2.2.2 Safety

STAGES I AND II:

Safety profile will be described after each injection for primary schedules and for booster dose.

The safety analysis will address the number and percentage of subjects with injection site reactions (pain, erythema, and swelling) from D0 and D07, solicited systemic reactions (fever, headache, malaise, myalgia, and asthenia) from D0 to D14, unsolicited AEs until D28, non-serious AESIs from D0 to D07, and unsolicited immediate systemic event occurring within 30 minutes after each injection. Solicited injection site reactions or solicited systemic reactions will be described according to time of onset, number of days of occurrence, action taken, and intensity.

Unsolicited AEs or non-serious AESIs will be described according to nature (MedDRA preferred term), time to onset, duration, intensity, action taken, and relationship to vaccination.

Unsolicited immediate systemic events will be described according to nature (MedDRA preferred term) and relationship to vaccination.

The number and percentage of subjects with SAEs, including serious AESIs will be described according to nature (MedDRA preferred term), seriousness criteria, outcome, and relationship to vaccination throughout the trial.

All AEs leading to study termination will be described according to nature (MedDRA preferred term) and relationship to vaccination.

Detection of symptomatic dengue cases

The number and percentage of subjects with a hospitalized VCD cases occurring during the trial after the injection will be described using safety analysis set.

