5.5 Determination of Sample Size and Power Calculation

[figure not shown]
A total of 1050 subjects are planned to be enrolled with a 1:1:1 enrollment ratio (350 per group [or 1:1:1:1:1:1 randomization ratio, 175 per subgroup]).

[REDACTED]

Table 5.2: Power of the study based on the Primary Objectives - STAGE I

Baseline Seropositive (%)	Population per group	Objectives	Endpoints	NI Margin	Power (%)
100%	296	Group 2 vs Group 1	28 days post-Inj 3 vs 28 days post-Inj 3	2	99.52
	296	Group 2 vs Group 1	1year post-Inj 3 vs 1 year post-Inj 3	2	95.20
90%	266	Group 2 vs Group 1	28 days post-Inj 3 vs 28 days post-Inj 3	2	98.94
	266	Group 2 vs Group 1	1year post-Inj 3 vs 1 year post-Inj 3	2	93.26
80%	235	Group 2 vs Group 1	28 days post-Inj 3 vs 28 days post-Inj 3	2	97.76
	235	Group 2 vs Group 1	1year post-Inj 3 vs 1 year post-Inj 3	2	89.22
70%	207	Group 2 vs Group 1	28 days post-Inj 3 vs 28 days post-Inj 3	2	95.78
	207	Group 2 vs Group 1	1year post-Inj 3 vs 1 year post-Inj 3	2	83.54
60%	178	Group 2 vs Group 1	28 days post-Inj 3 vs 28 days post-Inj 3	2	92.92
	178	Group 2 vs Group 1	1year post-Inj 3 vs 1 year post-Inj 3	2	75.64

Table 5.3: [REDACTED]

The following assumptions were considered:

- Alpha level of 2.5% (one sided) with a Bonferonni adjustment for multiplicity in Stage II
- Non-inferiority margin of 2 ($\log_{10} = 0.301$)

- [REDACTED]

- Dropout rate of 15%

The sample size will also provide a 95% probability of observing an AE that has a true incidence of $>0.85\%$ in each group (N=350).

For the measurement of the Cellular Immune Response, a convenience number of 60 subjects from a specific site in Colombia who consent to participate in additional immune response testing, the AIT subset, was selected, 10 subjects from each subgroup.

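### The any-dose safety rule classifies subjects by their first injection, which would label 700 of 1050 planned CYD recipients as placebo and merge the 1-dose and 2-dose schedules

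*SAP*

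**What the plan says.** SAP 5.2.3 and protocol 12.2.3 carry the same rule. A safety set is formed for each dose, and at that dose subjects are classified by what they received then. For summaries across doses: "For the analysis at any dose, subjects will be analyzed according to the treatment received at the first dose".

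The schedules are in SAP 3.1. Group 1 starts on CYD and stays on it for all three visits. The 2-dose arm is described thus: "Group 2 subjects (N = 350) will receive PLA at the first injection visit and CYD dengue vaccine at the last 2 visits". The 1-dose arm changes product one visit later, so that its only active injection is the third: "Group 3 subjects (N = 350) will receive PLA at the first 2 visits and CYD dengue vaccine at the last injection visit".

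Other relevant places in the SAP:

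- Section 5.2.2 (Full Analysis Set) names the group explicitly: "Subjects will be analyzed by the vaccine group to which they were randomized". Section 5.2.3 has no such wording.
- Section 5.5 states the safety precision (95% probability of seeing an AE with true incidence above 0.85%) "in each group (N=350", that is, for each of three groups.
- Section 4.4.2.3.2 sets a reporting period for SAEs: "During the study (i.e., all SAEs occurred during the study".
- Section 5.1.2.2.2.2 says that "hospitalized VCD cases occurring during the trial after the injection will be described using safety analysis set".
- Section 2.2 sets a safety objective that covers each injection and any injection.
- Section 5.7, the list of changes from the protocol, does not alter the any-dose rule.

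**The concern.** First-injection classification works when the product is constant within a subject. In this trial it changes for two of the three groups. A first injection of placebo does not show whether the subject belongs to Group 2 or Group 3, and does not show that CYD followed.

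An any-injection table built on the rule would therefore report events after CYD under a placebo heading, and would pool the two reduced-dose schedules that the trial was set up to study. This matters most for SAEs and hospitalised VCD over the whole trial. Protocol 1.3.2 records an increased risk of hospitalised or severe dengue in subjects seronegative before CYD. Protocol 1.4 notes that there are no data on whether that risk differs after partial vaccination. SAP 5.1.4 also asks for SAE tables by baseline dengue status. A column that mixes placebo time with time after one or two CYD doses would obscure what those descriptive tables are meant to show.

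**Working it through.** **The plan's own safety figure.** With n = 350 and incidence 0.85%, the chance of at least one event is 1 − (1 − 0.0085)^350 = 0.9496, against 95% stated. The inverse, 1 − 0.05^(1/350), is 0.852%. The figure reproduces, and it treats each schedule group of 350 as its own safety group. In a merged column of 700 the corresponding incidence is 1 − 0.05^(1/700) = 0.43%, which is not the stated design.

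**Classification under the literal rule** (schedules and planned N from SAP 3.1)

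| Group | N | Inj. 1 | Inj. 2 | Inj. 3 | Any-dose label | CYD doses planned |
|---|---|---|---|---|---|---|
| 1 | 350 | CYD | CYD | CYD | CYD | 1050 |
| 2 | 350 | placebo | CYD | CYD | placebo | 700 |
| 3 | 350 | placebo | placebo | CYD | placebo | 350 |

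- Columns: CYD 350; placebo 350 + 350 = 700.
- Planned CYD recipients labelled placebo: 700/1050 = 67%.
- Stage I CYD injections held by that column: (700 + 350)/2100 = 50%. This is a share of doses, not of events.
- If the planned 15% dropout all fell before the first CYD injection (an extreme case), 0.85 × 700 = 595 would be mislabelled. Those who left earlier would be correctly labelled placebo.

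**Follow-up time in Groups 2 and 3 after the first CYD injection** (nominal visit times; first CYD at month 6 in Group 2 and month 12 in Group 3)

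1. To the Year 1 visit (month 24, before any booster), complete follow-up: 350 × (18 + 12) = 10,500 of 350 × (24 + 24) = 16,800 subject-months, or 62.5%.
2. The same, with 15% leaving just before first CYD: time before CYD is 350 × (6 + 12) = 6,300; time after it is 0.85 × 10,500 = 8,925; 8,925/(8,925 + 6,300) = 58.6%.
3. To planned end of participation (month 30 in subgroup a, month 42 in subgroup b, 175 per subgroup): 175 × (24 + 36 + 18 + 30) = 18,900 of 175 × (30 + 42 + 30 + 42) = 25,200, or 75%. With the same dropout it is 16,065/22,365 = 71.8%. These two figures include time after the booster.

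**An alternative reading of the rule.** If first dose meant first CYD dose, every CYD recipient would fall into one class, and the three schedules would still not be separated.

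**The case against.** The best counter-argument is that treatment here means the arm, not the product. Protocol Table 5.1 has separate columns for treatment group and product received. SAP 3.1 and 5.1.3.2 call Groups 1 to 3 treatment arms or groups, and protocol 6.5 separates treatment allocation from the dispensing of doses. SAP 5.1.2.2.2.2 says safety is described for the primary schedules, and the precision statement is per group of 350. On this view three columns were always intended and the sentence is only badly worded.

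That is good evidence of intent. It does not rescue the rule. The sentence just before it in SAP 5.2.3 classifies subjects by what was received at a given dose, which can only be a product. Even on the arm reading, an as-received rule keyed to the first injection cannot assign a subject to Group 2 or Group 3, because both start with placebo.

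Three further objections stand in part:

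- The consequence is inferred, because no table is tied to the rule by name.
- Last vaccination is already derived for unsolicited AEs and SAEs (SAP 4.4.2.2.3 and 4.4.2.3.1), so event-level attribution is available. The any-dose rule does not use it.
- Some of the extra tabulation overlaps with existing output. Unsolicited non-serious AEs are analysed only within 28 days of an injection, and safety after the booster is already to be described.

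**Conclusion.** The concern holds. As written, the rule gives columns of 350 and 700, labels 67% of planned CYD recipients as placebo, and cannot distinguish the 1-dose from the 2-dose schedule. It is a stated rule that gives a wrong result, not a missing detail, and SAP 5.7 leaves it in place.

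The reach is limited. Per-injection tables carry the right product, and no hypothesis test depends on the rule. The counts rest on planned numbers with everyone reaching the first CYD injection; the time shares also assume nominal visit times. That SAEs during the study and hospitalised VCD are affected is a reasonable inference from their spanning several injections, but the documents do not state it. The rule should be corrected before the any-injection tables are produced.

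**What to change.** Replace the sentence in SAP 5.2.3 and protocol 12.2.3 with wording such as:

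> For the analysis after any injection, subjects will be presented by schedule group (Group 1, 2 or 3) according to the schedule actually received. Subjects whose injections are all consistent with their randomised schedule, including incomplete schedules, are presented in their randomised group. Subjects whose injections depart from their randomised schedule and fit no other single planned schedule are listed separately.

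In addition:

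- State which tables use the any-injection rule.
- Tabulate SAEs, hospitalised VCD and unsolicited AEs by product last received and by whether any CYD had been given. The derivation exists; for SAEs it reads: "If an SAE has a non-missing visit number, the visit number should be used to determine the last vaccination before the SAE". This adds most for SAEs and hospitalised VCD; for unsolicited AEs it largely repeats the per-injection tables.
- Show post-booster events separately in the any-injection tables.

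The cost is wording in two documents and the any-injection table shells. No new data are needed. If presentation by schedule was always intended, the change simply records it.

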5.2.4 Other Analysis Sets

Enrolled subjects set

Enrolled subjects are subjects for whom a CRF has been created.

Randomized subjects set

Randomized subjects are subjects who were randomly assigned to Group1a, Group1b, Group2a, Group2b, Group3a and Group3b.

AIT subset

The AIT subset is defined as those subjects who belong to the Randomized subjects set but had additional blood samples drawn for the assessment of CMI, additional neutralizing Ab titers (for exploration of the Ab response's kinetics), and Ab specificity and affinity maturation in the present trial. The AIT subset will include 60 randomized subjects from a specific site. Subjects will be analyzed by the vaccine group to which they were randomized.

5.2.5 Populations Used in Analyses

The PPAS will be used for the analysis for the primary objectives. The FAS will be used for the superiority hypotheses testing for secondary objectives. All other immunogenicity analyses will be performed on the FAS.

The SafAS will be used for the description of clinical safety.

Enrolled subjects and randomized subjects will be used for various standard population tables including duration of the study, disposition of participants and deviations. Demographic and baseline characteristics will be presented on the PPAS and FAS.

The AIT subset will be used to describe additional neutralizing Ab levels in this subset, Ab specificity and affinity maturation, and CMI responses.

^a for which safety data are scheduled to be collected

5.3 Handling of Missing Data and Outliers

5.3.1 Immunogenicity

The LLOQ and ULOQ management will be performed as described in [Section 4.4.1.1](#). Missing data will not be imputed. No test or search for outliers will be performed.

5.3.2 Safety

No replacement will be done unless state otherwise. No search for outliers will be performed.

In all subject listings, partial and missing data will be clearly indicated as missing.

5.3.2.1 Immediate

For unsolicited non-serious systemic AEs, a missing response to the “Immediate” field is assumed to have occurred after the 30-minute surveillance period and will not be imputed.

For SAEs, missing or partially missing elapsed time from last vaccination recorded if within 24 hours will remain missing and not be imputed. Such SAEs will not be considered as immediate.

5.3.2.2 Causality

Missing causality (relationship) for unsolicited non-serious AEs and SAEs will be considered at the time of analysis as related to vaccination.

5.3.2.3 Measurements

Missing measurement (for temperature or length) will not be replaced.

5.3.2.4 Intensity

For solicited reactions, missing intensities will be handled as described in [Section 4.4.2.1.1](#). For unsolicited non-serious AEs, missing intensities will remain missing and will not be imputed.

5.3.2.5 Start Date and Stop Date

Missing or partially missing start dates for unsolicited AEs will remain missing and not be imputed. If either the start or stop date is missing or partially missing, the time to onset will be considered to be missing. Nevertheless unsolicited AEs with missing time to onset will be included in analyses according to the visit collected.

Missing or partially missing stop dates for AEs (solicited reactions and unsolicited AEs) will remain missing and not be imputed.

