Subjects / Parents / Legally acceptable representatives are to measure body temperature once per day, preferably always at the same time. The optimal time for measurement is the evening, when body temperature is the highest. Temperature is also to be measured at the time of any apparent fever. The observed daily temperature and the route of measurement are to be recorded in the DC, and the highest temperature will be recorded by the site in the eCRF. The preferred route for this trial is axillary. Pre-vaccination temperature is also systematically collected by the Investigator on the source document for all subjects. Tympanic thermometers must not be used.

9.2.2.3.3 Unsolicited Non-serious Adverse Events From Day 0 to Day 28 After Each Vaccination

In addition to recording solicited reactions, subjects / subjects' parents / legally acceptable representatives will be instructed to record any other medical events that may occur during the 28-day period after injection. Space will be provided in the DC for this purpose.

For each unsolicited non-serious AE, the following information is to be recorded:

- Start and stop dates^a
- Intensity of the event:
 - For measurable unsolicited non-serious AEs that are part of the list of solicited reactions, the size of the AE as well as the temperature for fever will be collected and analyzed based on the corresponding scale used for solicited reactions (see [Table 9.1](#) and [Table 9.2](#))
 - Other unsolicited non-serious AEs will be classified according to the following intensity scale:
 - Grade 1: No interference with activity
 - Grade 2: Some interference with activity
 - Grade 3: Significant; prevents daily activity
- Action taken for each AE, if any (eg, medication)

The action taken by the subject / subjects' parent / legally acceptable representative to treat any **unsolicited AEs** will be classified in the eCRF using the following scale:

- 0: None
- 1: Medication (self-medication with an existing prescription or over-the-counter medication)
- 2: Health care provider contact (no new medication prescribed)

^a The stop date of all related AEs will be actively solicited. For other events, the investigator will provide the stop date when it becomes available. AEs for which no stop date was obtained during the course of the trial will be considered as ongoing at the end of the trial.

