4.4.2.2.4 Time of Onset

Time of onset is derived from the start date of the unsolicited non-serious AE provided in the clinical database and the date of last vaccination:

- Start date of the unsolicited non-serious AE - date of previous vaccination

The time of onset should be considered as missing only if one or both of the dates are missing or partially missing.

The unsolicited non-serious AEs will be analyzed “Within 28 days”, which corresponds to AEs with a time to onset between 0 and 28 days after vaccination or missing. An AE with missing time of onset will be considered to have occurred just after the vaccination indicated by the visit number, so will be included in these tables.

Note: Unsolicited non-serious AE that occurred before vaccination (negative time of onset) or with a time of onset higher than defined above will not be included in analysis, but will be listed separately.

Time of onset will be displayed by period as follows: D0-D3, D4-D7, D8-D14, \geq D15 and Missing.

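### SAP 5.3.2.5 blanks time to onset when only the stop date is missing, contradicting SAP 4.4.2.2.4 and placing some ongoing events in the wrong 28-day safety tables

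*SAP*

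**What the plan says.** Three sections of the SAP bear on a missing stop date.

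- **5.3.2.5 (Start Date and Stop Date)**: "If either the start or stop date is missing or partially missing, the time to onset will be considered to be missing". Such events stay in the analysis: "Nevertheless unsolicited AEs with missing time to onset will be included in analyses according to the visit collected". Stop dates are not filled in: "Missing or partially missing stop dates for AEs (solicited reactions and unsolicited AEs) will remain missing and not be imputed".
- **4.4.2.2.4 (Time of Onset)** gives the formula: "Start date of the unsolicited non-serious AE - date of previous vaccination". It then says: "The time of onset should be considered as missing only if one or both of the dates are missing or partially missing". The two dates in question are the start date and the date of the previous vaccination.
- **4.4.2.2.5 (Duration)** computes duration from the start and stop dates and makes duration missing when either is missing.

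What happens to a missing onset is set in 4.4.2.2.4. The 28-day table takes onset from 0 to 28 days, or missing: "An AE with missing time of onset will be considered to have occurred just after the vaccination indicated by the visit number". A known onset above 28 days, or before vaccination, is kept out of the analysis and listed separately.

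For SAEs, 4.4.2.3.2 uses the same onset method. SAEs collected after Visits 1, 3, 5, 7, 8 or 9 "with missing time of onset will be included in the table of SAEs analyzed" as within 28 days of the respective injection.

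Protocol 9.2.2.3.3 (footnote on start and stop dates) says: "AEs for which no stop date was obtained during the course of the trial will be considered as ongoing at the end of the trial".

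**The concern.** The stop date is not part of the onset formula, so 5.3.2.5 discards an onset that can be computed. The discarded value is not neutral, because missing onset is treated as falling inside the 28-day window. Whether a late event appears in the 28-day table or in the separate listing would then depend on whether it has ended, not on when it began.

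The records affected are foreseeable. An ongoing event has no stop date, and stop dates are not imputed. Chronic conditions of the kind the protocol names as examples of important medical events in 9.2.2.1 (new onset diabetes, autoimmune disease) may never receive one.

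SAP 5.4 plans four analyses at successive data cuts. An event that is ongoing at one cut and resolved by the next could change table with no change in its start date.

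At stake are the 28-day counts and the onset categories that describe the safety profile, which is a secondary objective.

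**Working it through.** The documents give no figure to reproduce, so the check applies both rules to the same records.

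**Inputs**
- Rule A (SAP 4.4.2.2.4): onset = start date − vaccination date; missing only if one of these is missing.
- Rule B (SAP 5.3.2.5): as rule A, but also missing if the stop date is missing.
- 28-day table (SAP 4.4.2.2.4): included if 0 ≤ onset ≤ 28 or onset is missing; otherwise listed separately.
- Onset categories (SAP 4.4.2.2.4): D0-D3, D4-D7, D8-D14, D15 or later, Missing.
- Scope: SAP 4.4.2 defines unsolicited AEs to include those on the SAE form, so 5.3.2.5 covers SAEs too.

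**Unsolicited AEs, vaccination on day 0**

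| Start | Stop | Rule A | Rule B |
|---|---|---|---|
| D10 | D14 | 10, in table (D8-D14) | 10, in table (D8-D14) |
| D10 | none | 10, in table (D8-D14) | missing, in table (Missing) |
| D28 | none | 28, in table (D15 or later) | missing, in table (Missing) |
| D29 | none | 29, listed separately | missing, **in table** |
| D35 | D40 | 35, listed separately | 35, listed separately |
| D35 | none | 35, listed separately | missing, **in table** |
| D42 | none | 42, listed separately | missing, **in table** |
| D−3 | none | −3, listed separately | missing, **in table** |
| missing | missing | missing, in table | missing, in table |

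The two D35 rows have the same start and differ only in the stop date. Under rule A both are listed separately. Under rule B the one without a stop date enters the 28-day table.

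**Reach for non-serious AEs.** They are collected for days 0 to 28 and reviewed at a visit 28 days after injection with a +14-day window, so by day 28 + 14 = 42 at the latest within the window. The late starts that can move are therefore mainly those in days 29 to 42, a span of 42 − 28 = 14 days. Starts before vaccination can also move.

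**Reach for SAEs.** SAP 4.4.2.3.2 sends a missing onset to the 28-day table only if the SAE was collected after Visits 1, 3, 5, 7, 8 or 9. V02, V04, V06 and V10, which close the post-injection periods, are not on that list. After injection 3, for a subject who attends V06 on schedule, only the interval from V05 to V06 (28 to 42 days) can feed the 28-day table through this route. An SAE found later, by telephone or at Y1 V07, is collected after V06 and does not enter it.

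**The case against.** The strongest reply is that the SAP already contains the right rule. Section 4.4.2.2.4 is the derivation section, its restriction to the start and vaccination dates is explicit, 4.4.2.3.2 extends it to SAEs, and 4.4.2.2.5 keeps a missing stop date to duration. A programmer who follows those sections misplaces nothing. This stands in part: the error arises only if 5.3.2.5 is the section programmed. But 5.3.2.5 is the section headed for missing dates and a natural place to look, and SAP 5.7 does not resolve the conflict.

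The reply on reach also stands.

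- The window for late non-serious AEs is short, and the same protocol footnote says that stop dates of related AEs are actively sought, which reduces the number missing.
- Ongoing events that began within 28 days stay in the correct table and lose only their category.
- The table of SAEs during the study does not depend on the 28-day split.
- No immunogenicity hypothesis is touched.

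A reader might infer something stronger: that an ongoing SAE starting months after V05 would be reported as within 28 days, and that the true window is then only 28/365, about 8%, of the time feeding that table. The documents do not support this. In a subject who attended V06, such an SAE is collected after V06, which 4.4.2.3.2 leaves out, so 365 days is not the relevant denominator. A long interval could arise only outside the normal visit flow, for example if V06 was missed.

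**Conclusion.** The contradiction is real, and 5.3.2.5 is wrong as written. If it is programmed, three things follow:

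- ongoing unsolicited AEs with a known start after day 28 (mainly D29-D42) or before vaccination enter the 28-day tables instead of the listing;
- ongoing SAEs with such starts do the same if collected after Visits 1, 3, 5, 7, 8 or 9;
- ongoing events that began on days 0 to 28 are shown with onset Missing.

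The size cannot be computed, because the documents give no count of events with a start date and no stop date. It is probably small, given the 14-day span for late starts and the visit limit for SAEs. The conclusion assumes that closing visits take place within their windows and that visit numbers are recorded as planned. The consequence is confined to descriptive safety tables. This is a consistency correction worth making because it is nearly free, not a threat to the trial's main conclusions.

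**What to change.** In SAP 5.3.2.5, delete the reference to the stop date from the onset sentence. It should say that onset is missing only if the start date or the vaccination date is missing or partially missing, and that a missing stop date affects duration only. This brings 5.3.2.5 into line with 4.4.2.2.4 and 4.4.2.2.5.

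The cost is one sentence in the SAP and a check that the safety programs derive onset from the start and vaccination dates alone. No new data are needed. If tables have already been produced, rerun the 28-day tables and onset categories and compare them for events with a start date but no stop date. That comparison also gives the number affected.
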